There is currently limited information regarding the role of blood management in the benign gynecologic population and specifically, in patients who are scheduled to undergo surgery for fibroids and/or abnormal uterine bleeding. A thorough search through PubMed and clinicaltrials.gov did not reveal any studies on this issue. In 2019 at CCF only 2% of gyn patients at Main Campus were referred to blood management, but 12.6% of the main campus gyn population had a Hb of <10.0 g/dL. The overall goal of this study is to evaluate the role of preoperative blood management in optimizing surgical outcomes by reducing the co-morbidities associated with postoperative blood transfusion.

Specific Aims/Objective:

The primary objective of this study is to compare the change in baseline hemoglobin levels in patients in the study (Blood Management Protocol) and control ("usual care")

group who are undergoing hysterectomy for abnormal uterine bleeding. Change in baseline hemoglobin levels is defined as the difference of the hemoglobin level obtained within 72 hours prior to surgery and the hemoglobin level at 4 weeks postoperatively.

Our secondary objectives include 1. To evaluate the perioperative outcomes between the two groups including OR times, EBL, peri-operative transfusion rates, length of hospital stay, complications including intra-operative injuries, postoperative infection rates, readmission, and re-operation; 2. to assess patient satisfaction regarding their experience with the Blood Management protocol and extra outpatient infusion visits required using a patient questionnaire (PATSAT 35, Attached); and 3. to compare the quality of patient health and recovery between the two groups using the RAND-36 (Attached) assessment tool. The REDCap database will include potential identifiers to enable online surveys. The included potential patient identifiers include: date of birth, surgery date, and subject email (they provide for the study.)

Data variables that will be collected in the study are visible in the following table.

Patier	nt Demographics:
•	MRN
•	Age/ Date of Birth
•	BMI

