Race • Gravidity/Parity Prior abdominal surgery Prior cesarean section Diabetes Hypertension **Current Smoker** Former Smoker • Menopause status Type of surgery: Hysterectomy or myomectomy Type: Vaginal, laparoscopic, open, laparoscopic assisted vaginal hysterectomy, robotic • Surgery date, discharge date • Surgery date/ Discharge date • Subject email Primary objectives: • Change in hemoglobin levels o Baseline Hemoglobin (pre-op) o Post Op Hemoglobin level Secondary objectives: • Operative time Blood Loss • Perioperative transfusion rate • Length of hospital stay • Intraoperative Complications o Intraoperative injuries o Post-operative infection rates Readmission Reoperation • Patient Satisfaction • Quality of Health and Recovery • Number of infusions received • Days on PO iron therapy

Table 1.0 -- Data Collection Variables

We anticipate that patients undergoing blood management protocol will have a faster return to normal recovery and better quality of life scores during recovery using the RAND-36 assessment questionnaire compared to patients undergoing usual care. We also plan to evaluate additional cost of blood management treatments for oral iron, IV iron, and blood transfusion in regards to feasibility, and from a health care utilization standpoint.

Methods and Study Design:

This will be a prospective randomized control trial conducted in a single large-referral center where anemic patients undergoing hysterectomy for fibroids or abnormal uterine bleeding will be recruited and randomized to undergo Blood Management protocol or usual care.

Inclusion criteria are anemic patients (defined as Hgb ≤ 11g/dL within 30 days of initial MIGS consult visit), greater than 18 years of age, with abnormal uterine bleeding, or fibroids undergoing hysterectomy by laparoscopic, robotic, vaginal or open routes. Exclusion criteria are malignancy, pregnancy, sickle cell anemia or other blood dyscrasias, women who received blood transfusions in 30 days prior to surgery, women receiving EPO therapy, women who have undergone gastric bypass surgery, and women on therapeutic/full anticoagulation. Patients undergoing hysteroscopic myomectomy alone without will not be included in the study.

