The intervention will include pre-surgical optimization blood management referral based on preoperative Hb levels ≤11.0. Currently it is not standard of care at the Cleveland Clinic to send all patients with Hb ≤11.0 due to secondary anemia to blood management. It is done currently at the provider/surgeons preference alone and not through a research protocol or guidelines. At the initial consultation visit a CBC will be drawn, patients will be given a consent form for the study and asked to review it. If a Hb ≤11.0 within 30 days of consultation visit is documented in EPIC, they will be consented and randomized at the consultation visit. All patients after initial consultation visit will be immediately sent to the lab for blood draw if they have not had Hb drawn within 30 days. Lab draw includes: CBC + differential, iron studies: iron, TIBC, ferritin, optional B12. If the initial consult visit occurs at Fairview or Hillcrest Hospital, the patient's follow up preoperative visit will be scheduled at the main campus where consent will be obtained. The blood management team then will receive the referral from primary surgeon's office via EPIC inbasket. Blood management coordinator will assess patient, arrange treatment, and orders will be cosigned by surgeon/referring provider. Blood management may further assess for symptoms of PICA, restless legs, and cold intolerance as symptomatic indicators of anemia. The Rand 36 study will be administered at either the consultation or the pre-operative visit. The PATSAT 35 will be administered at the postoperative visit only. Postoperative Hb levels will be collected by a CBC at the post-operative visit. All postoperative visits will be scheduled at the main campus. All surveys and consents will be obtained at visits that occur at the main campus.

[figure not shown]

Table 2: Blood Management Preoperative Iron Deficiency Algorithm

Blood loss intraoperatively will be measured as accurately as possible with suction device recording and quantitative blood loss and tapes/packs by weighing instead of only visual assessment.

[figure not shown]

Image: 1.0 -- Patient Flow Sheet

Justification for Sample Size:

Power Calculation:

Sample size was calculated to have 80% power to detect a difference between groups using a T-test at a significance level of 0.05. We assume that patients at 4 weeks will have a standard deviation in hemoglobin values of 1.2 g/dL (8) to detect a 1 g/dL difference between groups, we

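### The plan predicts faster recovery by RAND-36, but its readable text schedules no RAND-36 after surgery and gives no method for time or trajectory, so speed cannot be tested and level may go unmeasured.

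*Combined protocol and SAP*

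**What the plan says.** Specific Aims/Objective lists as its third secondary objective "to compare the quality of patient health and recovery between the two groups using the RAND-36". It gives no assessment times. The paragraph after Table 1.0 goes further and anticipates that women on the blood management protocol "will have a faster return to normal recovery and better quality of life scores during recovery", by the RAND-36, compared with usual care. Table 1.0 has a line for quality of health and recovery, without times, and no time-to-recovery variable.

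The survey schedule is under Methods and Study Design. For the RAND-36: "The Rand 36 study will be administered at either the consultation or the pre-operative visit". For the satisfaction questionnaire: "The PATSAT 35 will be administered at the postoperative visit only". On place: "All surveys and consents will be obtained at visits that occur at the main campus". The same paragraph says of the blood count: "Postoperative Hb levels will be collected by a CBC at the post-operative visit". It does not date that visit. Specific Aims/Objective sets the postoperative hemoglobin at 4 weeks.

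On survey mode, Specific Aims/Objective adds: "The REDCap database will include potential identifiers to enable online surveys". The woman's email address is among those identifiers. No online schedule is given.

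The Analysis plan names two-sample t-tests, Wilcoxon rank sum tests, and chi-square or Fisher's exact tests.

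**The concern.** The prediction has two parts: how quickly women recover, and how they score while recovering. Both need RAND-36 readings after surgery. Speed needs either several readings or a defined recovery event with a date. The readable schedule provides neither.

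At stake is a named secondary objective. If staff follow the schedule literally, the RAND-36 data describe women before their operation and say nothing about recovery. If staff add one reading at the postoperative visit on their own initiative, the trial has a comparison of status at that visit, which could be mistaken for evidence about speed. A difference at one visit would not establish faster recovery, and no difference would not rule it out. The postoperative reading cannot be recovered later for women who have already passed that visit.

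**Working it through.** No figure in the plan relates to this endpoint. The only sized comparison is hemoglobin, and it reproduces: a difference of 1 g/dL with SD 1.2 g/dL, alpha 0.05 (two-sided assumed) and 80% power gives 23.60 per group by the exact t-test, rounded up to 24, or 48 in total. Then 48 / (1 − 0.20) = 60. Nothing below changes this.

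**1. Count the RAND-36 readings in the readable text.**

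- Before surgery: one, at either of two visits.
- After surgery: 0 stated. The PATSAT 35 is the only survey placed there.
- After surgery, if the described postoperative visit is also used for the RAND-36: 1.

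**2. Ask what each count allows.**

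- With 0 postoperative readings, the arms can be compared only before surgery. Neither level nor speed of recovery is observed.
- With 1 reading at a common time T, the arms can be compared on status at T, or on change from the pre-surgery score. If R is the time at which a woman is back to normal, this reading shows at best whether R ≤ T or R > T. Two arms with the same share recovered by T can differ in how soon they got there. Even this needs a definition of normal recovery, which the plan does not give.
- With 2 or more fixed postoperative times, the course of recovery can be compared. No readable section schedules this.

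**3. Check the analysis.** Every method in the Analysis plan is a two-group comparison of a single measure. None handles repeated scores or time to an event.

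**4. Check when the postoperative visit falls.** The hemoglobin is drawn at the postoperative visit and is defined at 4 weeks, so that visit is probably near 4 weeks. This is an inference.

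**5. See what one reading could detect.** For an unadjusted two-sample t-test, two-sided 0.05 and 80% power, the detectable difference is 0.83 SD with 24 per arm and 0.74 SD with 30 per arm. A single-time RAND-36 comparison is feasible, but a non-significant result would leave moderate differences open.

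**The case against.** The strongest reply is that the schedule may be complete in a place that cannot be read. The Patient Flow Sheet (Image 1.0) is not shown and could give RAND-36 times after surgery. The text also refers once to postoperative visits in the plural. This stands as a limit on certainty: the point concerns the readable text.

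Second, the speed statement is an expectation, while the formal objective is only a comparison of health and recovery. The RAND-36 might be meant to serve only the quality-of-life half of the sentence. Length of stay, discharge date and readmission are collected and bear on early recovery. All of this is fair and lowers the weight of the speed claim. It does not supply the postoperative RAND-36 that the formal objective itself needs, and the plan names none of those other variables as its measure of return to normal.

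Third, the endpoint is secondary and unpowered, so an elaborate set of early surveys is a preference. Agreed: the early surveys are needed only if the speed claim is kept.

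A reader might also infer three stronger things that the documents do not support.

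- *That holding surveys at main-campus visits is the cause.* Place is not the main gap; the missing postoperative RAND-36 time is.
- *That the plan plainly contradicts itself on survey mode.* An online survey can be completed during a visit, so the two statements are unclear together and need reconciling.
- *That a reading near 4 weeks is the least sensitive place to look.* The documents give no recovery curve, and the answer turns on what is assumed. Take the recovered fraction as 1 − 2^(−t/h), with t and half-time h in weeks. Half-times of 1.0 versus 1.5 give arm differences of 0.130, 0.147 and 0.095 at weeks 1, 2 and 4, so week 4 is smallest. Half-times of 2 versus 3 give 0.087, 0.130 and 0.147, so week 4 is largest.

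**Conclusion.** The concern holds in a limited form. On the readable text there are no stated postoperative RAND-36 readings, at most one if the described postoperative visit is used, and no longitudinal or time-to-recovery analysis. Speed of recovery by RAND-36 therefore cannot be tested. Without a postoperative reading, level of recovery cannot be compared either.

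This rests on two assumptions: that the missing flow sheet adds no RAND-36 times, and that there is one postoperative study visit. If the flow sheet gives one postoperative time, the level comparison is rescued but the speed claim is not. If it gives several, what remains is the missing definition of normal recovery and the missing analysis method. The scope is one secondary objective; the primary endpoint is untouched. It should be corrected, because the change is cheap and unscheduled readings cannot be collected afterwards.

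**What to change.** - **Schedule.** Under Methods and Study Design, state that every randomized woman, in both arms, completes the RAND-36 before surgery and again at one fixed postoperative time, for example with the 4-week hemoglobin. Allow completion by the REDCap email link or at the visit. The pre-surgery reading is best taken at the consent visit before allocation is known, because a later one may already reflect anemia treatment. Make the flow sheet agree.
- **Survey mode.** Reconcile the online-survey statement in Specific Aims/Objective with the visit-based statement in Methods and Study Design, so that it is clear which surveys may be completed away from the clinic.
- **Analysis.** In the Analysis plan, compare the arms on the postoperative RAND-36 score adjusted for the pre-surgery score, and report the difference with a confidence interval.
- **Claim.** After Table 1.0, reword the expectation to better RAND-36 scores at the postoperative assessment and remove the statement about speed. Keep it only if early emailed surveys at fixed times and a repeated-measures comparison are added.

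Rewording alone is not enough, because no readable section schedules the postoperative RAND-36 that the new wording would refer to. The cost is a protocol edit, a REDCap schedule, one more short survey per woman, and some mixing of online and in-clinic completion. The sample size does not change.

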In addition to the high incidence of secondary anemia in patients with abnormal uterine bleeding and fibroids, surgeries for abnormal uterine bleeding and fibroids such as hysterectomy and myomectomy can involve a significant blood loss (4,5). The overall rate of postoperative blood transfusion for hysterectomy in the cited study was 13.3% (5). The need for packed red blood cell transfusion is one of the known complications of surgery and is increased in women who are noted to be anemic preoperatively. Blood transfusions are associated with increased adverse surgical outcomes. Higher rates of morbidity and mortality have been reported in patients receiving one unit of packed red blood cells compared with patients who did not undergo transfusion (6). The WHO recommends, in compliance with their guide for optimal clinical use, "that before surgery every reasonable measure should be taken to optimize the patient's own blood volume" (7). Pre-operative hemoglobin less than 10.6 g/dL versus greater than or equal to 13.1 g/dL had five times the odds of transfusion (5).

Anemia is a modifiable risk factor that can be assessed and optimized pre-operatively. Prior studies have evaluated preoperative blood management strategies in oncology patients, patients undergoing general surgery procedures, and orthopedic surgery. A systematic review of the management of perioperative anemia showed varying results in change in hemoglobin levels after blood management intervention, but all studies were able to show a decrease in postoperative blood transfusions (8). A randomized control trial evaluating oral iron supplementation preoperatively in patients undergoing colorectal surgery reported reduced blood transfusion rates in the group receiving this intervention (9). Froessler et al studied perioperative IV iron intervention in patients undergoing major abdominal surgery in a randomized control trial with using blood transfusions as a primary endpoint. They concluded that perioperative IV iron reduced the need for blood transfusion and was also associated with higher postoperative hemoglobin and shorter hospital stay (10). A blood management protocol implemented in the perioperative period also noted a decrease in perioperative blood transfusion and postoperative anemia in the orthopedic population. The interventions used in their blood protocol management included erythropoietin, ferric carboxymaltose, and tranexamic acid (11).

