will need 48 patients total (24 per group) if the groups are of equal size. Assuming a 20% dropout rate, 60 patients total (30 per group) will be the target enrollment.

Cost and Payments to Subjects

The patients will have no additional costs due to participating in the study beyond the usual insurance copays and standard costs for appointments.

Quality Control Procedure:

Information will be provided to all department members involved in administration of the study. Follow up, data entry, and patient follow up will be closely followed by the research team (resident, fellow, staff physicians, MIGS NP's, Lead research nurse)

Process of Consent

Patients would be consented for participation in the study at their primary surgeon's office when shared decision making for proceeding with surgery is performed. Patients will receive no difference in care based on their participation in the study apart from the study protocol

Risks and Discomfort of the Project

The study has been designed to minimize as much risk as possible, and participants will be subjected to no more than minimal or standard risk for undergoing the intervention. Breach of confidentiality is a small risk. Physical risk are rare and unanticipated but would be limited to transfusion reaction to the IV iron therapy. There are no psychological risks for patients who participate in this study. Participants can also benefit from their participation in this study due to their altruistic motivation for partaking in research study they have contributed to scientific advancement.

Analysis plan

Approximately normally-distributed continuous measures will be summarized using means and standard deviations and will be compared using two-sample t-tests. Continuous measures that show departure from normality and ordinal measures will be summarized using medians and quartiles and will be compared using Wilcoxon rank sum tests. Categorical factors will be summarized using frequencies and percentages and will be compared using Pearson's chi-square tests or Fisher's Exact tests. All analyses will be done using SAS (version 9.4, The SAS Institute, Cary, NC) and a p < 0.05 will be considered statistically significant.

Timetable:

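### The cost evaluation names no cost summary; the default median/Wilcoxon rule does not measure total cost and can call blood management costlier when mean cost is equal or lower

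*Combined protocol and SAP*

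**What the plan says.** The cost aim is one sentence in the Specific Aims/Objective section, after Table 1.0: "We also plan to evaluate additional cost of blood management treatments for oral iron, IV iron, and blood transfusion in regards to feasibility". It goes on to add a health care utilization standpoint. It gives no cost measure, price source, time horizon or summary statistic.

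The only analysis rule is in the Analysis plan section. Approximately normal continuous measures get means and t-tests. For the rest, "Continuous measures that show departure from normality and ordinal measures will be summarized using medians and quartiles", with Wilcoxon rank sum tests. Cost is neither assigned to this rule nor exempted from it.

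The other relevant facts are:
- **Usual care** (Methods and Study Design) is no therapy or oral iron, so it contains no IV iron by definition.
- **Blood management** (Background) may mean observation, oral iron or IV iron. The share receiving IV iron is not given.
- **Transfusion** (Background): "The overall rate of postoperative blood transfusion for hysterectomy in the cited study was 13.3" percent. The same section reports five times the odds of transfusion for hemoglobin below 10.6 g/dL against 13.1 g/dL or more.
- **Table 1.0** lists a transfusion rate, the number of infusions and days on oral iron. It lists no red cell units, iron product, iron dose, visit count or price.
- **Specific Aims** refers to "extra outpatient infusion visits required" under patient satisfaction, but visits are not among the three cost items.

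**The concern.** A utilization question asks what each strategy costs in total for the women allocated to it. Total cost is the number of women times the mean, and neither a median nor a rank sum recovers it.

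Cost per woman here will have many values at or near zero, a cluster at the price of IV iron in one arm only, and a few large values from transfusion. Such data would be judged non-normal, so an analyst who follows the plan would use medians and Wilcoxon. The hoped-for saving comes from a few avoided transfusions, while the added cost is spread over many women who receive IV iron. Ranks register how many women cost more, but not by how much. The analysis could therefore report blood management as costlier when its mean cost is equal or lower.

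The recorded data add a second problem. A transfusion rate cannot be priced without the units given, and an infusion count cannot be priced without product and dose. Leaving out the referral and infusion visits would understate the cost of the blood management arm.

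**Working it through.** **1. Arm size.** The documents state no figure for cost, so the check uses the trial's own size. The plan assumes "80% power to detect a difference between groups using a T-test at a significance level of 0.05" and "standard deviation in hemoglobin values of 1.2 g/dL (8) to detect a 1 g/dL difference between groups". The normal approximation gives n per arm = 2 × (1.96 + 0.842)² × 1.2² / 1² = 22.6, rounded up to 23. The two-sided t-test gives 23.6, rounded up to 24, with 80.7% power. This agrees with "will need 48 patients total (24 per group) if the groups are of equal size". Dropout: 48 / 0.8 = 60, which agrees with "Assuming a 20% dropout rate, 60 patients total (30 per group) will be the target enrollment". Cost would be compared with 24 to 30 women per arm.

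**2. Does the median contain any transfusion cost?** With 24 women, the median transfusion cost is zero if at most 11 are transfused. The binomial probability of that is above 0.9999 at 13.3%, 0.993 at 25% and 0.787 at 40%. Applying the fivefold odds to 13.3% gives an assumed upper anchor for usual care: odds 0.133/0.867 = 0.153; × 5 = 0.767; 0.767/1.767 = 43%. That is still below one half, so the expected usual-care median holds no transfusion cost.

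**3. Simulation with equal true means.** All cost inputs are assumptions: 1 to 3 units per transfused woman; 1 to 3 infusions per IV-treated woman; one infusion costs 1; oral iron costs 0.02 and is taken by half of the women not on IV iron. Let q be the IV iron share and p₁, p₂ the transfusion risks in usual care and blood management. The price per blood unit that equalizes the means is

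T = [2q + 0.01(1 − q) − 0.01] / [2(p₁ − p₂)].

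For example, q = 0.8 with 13.3% vs 5% gives T = 1.592/0.166 = 9.59. At q = 0.2 with 40% vs 15%, T = 0.398/0.5 = 0.80.

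The table shows the percentage of 2000 simulated trials (24 per arm) in which two-sided Wilcoxon at 0.05 called blood management costlier. The nominal rate in that direction is 2.5%.

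| Transfused, usual care vs blood management | q = 20% | q = 30% | q = 50% | q = 80% |
|---|---|---|---|---|
| 13.3% vs 5% | 8 | 19 | 55 | 95 |
| 30% vs 10% | 2 | 5 | 15 | 47 |
| 40% vs 15% | 1 | 2 | 8 | 22 |

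In the same scenarios a comparison of means (Welch) did so in about 2% to 7% of trials, and in up to 11% if transfusion fell from 13.3% to zero. At 40% vs 15% and q = 20%, Wilcoxon called blood management cheaper in 5%, a slight reversal. Across all scenarios run with 24 or 30 per arm, the blood management median was the higher one in 70% to 79% of trials at q = 50% and in 86% to 100% at q = 80%.

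**4. Blood management truly cheaper.** At 30% vs 10% with blood priced at 1.5 times break-even, Wilcoxon still called blood management costlier in 12% of trials (q = 50%) and 48% (q = 80%).

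**5. A second price model.** Assumed: mean cost 12 per transfused woman, 1.5 for IV iron in 70% of the blood management arm, 0.1 for oral iron.
- At 13.3% vs 5%, with half of the women not on IV iron taking oral iron, the mean difference is 0.7 × 1.5 + 0.3 × 0.5 × 0.1 − 0.5 × 0.1 − 0.083 × 12 = 0.02. Under most oral iron shares tried, Wilcoxon called blood management costlier in 87% to 98% of trials. If every usual-care woman but no blood-management woman outside IV iron takes oral iron, a rerun of this model gives about 40%. A trivial cost can thus drive a rank test.
- At 25% vs 10%, the same sum with 0.15 × 12 gives −0.785, so blood management is cheaper. With half taking oral iron, Wilcoxon still called it costlier in roughly half to two-thirds of trials.

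**The case against.** The strongest reply is that the plan never assigns Wilcoxon to cost. Cost is not among the primary or numbered secondary objectives, Table 1.0 has no cost variable, and the Analysis plan also offers means and t-tests. A reader might infer that a rank test of cost is prescribed. The documents support only that it is the default for data that will almost surely be judged non-normal. That correction stands, but it leaves the cost analysis either unspecified or on the wrong footing.

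A reader might also infer that savings from avoided transfusions cannot appear at all. They usually cannot move the median, but transfused women take the highest ranks, so fewer transfusions do lower the arm's rank sum. Transfusion rates are also compared directly as a secondary outcome.

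On data scope, several replies are fair:
- Table 1.0 does record days on oral iron.
- The infusion count already approximates infusion visits.
- Length of stay, readmission and reoperation are utilization measures in their own right.
- The laboratory panel is not clearly created by allocation. The Background links it to the referral, but Methods sends every patient without a recent hemoglobin for a draw that includes iron studies.
- The record number is collected, so missing items might be retrievable later.

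None of this supplies blood units, iron product and dose, or a price source.

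**Conclusion.** The point holds as a gap in a side aim that should be closed. No cost summary is specified, and the rule that would apply by default does not estimate total cost. It can mislead against blood management when IV iron is common and transfusion uncommon.

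The size is uncertain. A reader might take a figure above 90% as the expected error rate, but the documents do not support that. It needs an IV iron share of about 70% to 80%, transfusion of 13.3% vs 5%, and assumed prices and oral iron use. The 13.3% is an overall hysterectomy rate, whereas this trial enrols women at or below 11 g/dL, whose risk is probably higher. With more transfusion and little IV iron, the distortion disappears or slightly reverses. What does not depend on prices is that the median will usually omit transfusion cost and that Table 1.0 lacks inputs needed to price the three items.

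The primary hemoglobin comparison and its sample size are unaffected.

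**What to change.** In the Analysis plan, exempt cost from the median/Wilcoxon rule. Report arithmetic mean cost per randomized woman by arm and the mean difference with a bootstrap 95% CI, from randomization to the 4-week visit.

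In Table 1.0, add red cell units transfused, iron product and dose, and blood management visits. Infusion visits can be taken from the infusion count already listed. Cost the referral and infusion visits, and laboratory tests as actually drawn in both arms, from one stated price source.

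The cost is one paragraph and a few record-derived fields. The interval will be wide with 24 to 30 women per arm, so a firm cost conclusion is unlikely, and the report should say so.
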